3.3.2 Secondary Outcome Measures

- Proportion of relapse free patients at months 3, 6, and 9
- Annualized Relapse Rate (ARR)
- Mean time to first relapse on OCR
- Proportion of patients free from MRI evidence of MS disease activity at months 3, 6, and 12
- Proportion of patients with new or enlarging T2 lesions at 3, 6, and 12 months. For patients with new or enlarging lesions, the number of new and enlarging lesions
- Proportion of patients with new Gd+ lesions at months 3, 6, and 12. For patients with new Gd+ lesions, number of new Gd+ lesions detected at months 3, 6, and 12.
- Change in the EDSS score from baseline to month 12.
- Change in MSIS-29 from baseline to months 6 and 12
- Number and type of AEs and SAEs
- Proportion of patients that discontinued OCR

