- Concomitant medications and adverse events (not required to be reviewed with the patient in person if Baseline is within 7 days of Screening visit, collect via chart review)
- OCR administration (300mg, 2 administrations: Day 0 and Day 14 ± 2 days)

Visit 3/3 Month Visit (Day 84 +/- 14 days from Baseline Day 0)

The following clinical and laboratory evaluations will occur 84 days from Baseline with a +/- 14 day window.

- Vital signs
- Neurological exam
- Relapse assessment
- EDSS
- Laboratory assessments: CBC, CMP, Pregnancy test (female only)
- MRI
- Concomitant medications and adverse events

Visit 4/6 Month Visit (Day 168 +/- 14 days from Baseline Day 0)

The following clinical and laboratory evaluations will occur 168 days from Baseline with a +/- 14 day window.

- Vital signs
- Neurological exam
- Relapse assessment
- EDSS
- MSIS-29
- Laboratory assessments: CBC, CMP, Pregnancy test (female only)
- MRI
- Concomitant medications and adverse events
- OCR administration (600mg)

Visit 5/9 Month Visit (Day 252 +/- 14 days from Baseline Day 0)

The following clinical and laboratory evaluations will occur 252 days from Baseline with a +/- 14 day window.

- Vital signs
- Neurological exam
- Relapse assessment
- EDSS
- Laboratory assessments: CBC, CMP, Pregnancy test (female only)
- Concomitant medications and adverse events

Visit 6/12 Month Visit (Day 336 +/- 14 days from Baseline Day 0)

The following clinical and laboratory evaluations will occur 336 days from Baseline with a +/- 14 day window.

- Vital signs
- Neurological exam
- Relapse assessment
- EDSS
- MSIS-29
- Laboratory assessments: CBC, CMP, Pregnancy test (female only)
- MRI
- Concomitant medications and adverse events
- OCR administration (600mg)

End of Study (EOS) Phone Contact (30 days +/- 14 days from study discontinuation)

The following clinical evaluation will occur 30 days +/- 14 days from study completion (12 Month OCR administration) or premature termination visit:

- Adverse events

Premature Termination Visit

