4.9.3 Efficacy Analysis

a. Primary Endpoint

Proportion of patients relapse free at 12 months after switching from NTZ to OCR

b. Secondary Endpoints

- Proportion of patients relapse-free at 3, 6, and 9 months after switching to OCR
- Mean time to first relapse
- MRI evidence of MS disease activity
- Proportion of patients with New or Enlarging T2 lesions at 3, 6, and 12 months. For patients with New or Enlarging T2 lesions, number of New and Enlarging T2 lesions.
- Proportion of patients with New Gd+ lesions detected at months 3, 6, and 12. For patients with New Gd+ lesions, number of New Gd+ lesions
- Annualized relapse rate (ARR)
- Change in EDSS from baseline to 12 months
- Change in MSIS-29 from baseline to 6 and 12 months

All patients that followed protocol will be used to evaluate the proportion of patients relapse-free at 3, 6, 9, and 12 months, mean time to first relapse, and ARR. This includes those that discontinued early but followed protocol up to discontinuation. All patients that followed protocol and did not discontinue will be used to evaluate MRI

evidence of MS disease activity at 3, 6, and 12 months, the change in MSIS-29 from baseline to 6 and 12 months, and the change in EDSS from baseline to 12 months.

A full analysis set consistent with the intent-to-treat (ITT) principle will also be used to analyze the proportion of patients relapse-free at 3, 6, 9, and 12 months, mean time to first relapse, and ARR using all subjects. Subjects who entered the trial and did not meet inclusion criteria may be excluded.

Summary statistics will be presented for continuous variables (mean, standard deviation, median, range) and categorical variables (counts and percentages). All analyses will use two-sided confidence intervals and p-values at the 0.05 significance level.

Primary Analysis

Kaplan-Meier survival analysis methodology will be used to determine the proportion of patients relapse-free at months 3, 6, 9, and 12. Median and mean time to first relapse with confidence intervals will be reported. Log rank tests and graphical presentations of Kaplan Meier curves with confidence intervals will be used to examine effects of center, gender, categorized age, categorized EDSS and duration of disease on survival distribution.

Secondary Analysis

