4.9.5 Missing Data

Demographic information and baseline disease for patients who followed protocol and completed the study, violated protocol, and discontinued the study will be reported separately and compared. The reasons for discontinuing or violating protocol and the patient's time on drug at occurrence will be reported and any influence on the trial results will be discussed. To assess the comparability between centers, summaries will be reported for all patients overall and by study center. Any other irregularities that result in missing data will be fully identified and discussed.

For the per protocol and full analysis sets, missing data due to discontinuation will be incorporated as censored time points in the survival analysis of relapse-free patients and ARR will be calculated using the range of time that the individual was in the study. If interim time points at 3, 6, or 9 months are missing, only the time points available will be used in the survival analysis. No relapse data will be missing at baseline, since only patients relapse free for six months are included. For the Kaplan Meier analyses and

log rank tests stratified by age, gender, EDSS, and center, we expect these patient characteristics to be non-missing. However, if they are missing, a complete case analysis per variable will be used and the number of missing will be reported.

For the analysis of the change in EDSS and MSIS-29, a complete case analysis with per protocol patients will be used.

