4.9.6 Determination of Sample Size

The sample size was based on a Kaplan Meier analysis with proportion of patients relapse free at 12 months as the primary endpoint. Assuming a relapse-free proportion of 0.80 at 12 months, 45 patients are required to say that the relapse free proportion is no lower than 0.68, with 95% confidence. To account for 10% attrition, a total of 50 patients are needed.

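### Mean time to first relapse cannot be estimated as labelled: any printed value is a restricted mean, and the plan does not name its horizon

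*Combined protocol and SAP*

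**What the plan says.** The secondary outcomes in section 3.3.2 include "Mean time to first relapse on OCR". Under the primary analysis in section 4.9.3, the plan adds: "Median and mean time to first relapse with confidence intervals will be reported". The mean is wanted in two analysis sets. One is the per-protocol set. The other is the full analysis set, which is to be used for the proportion "relapse-free at 3, 6, 9, and 12 months, mean time to first relapse, and ARR using all subjects".

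Three other places determine what the data can support:

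- **Follow-up (section 4.5.1).** The last scheduled relapse assessment is at "Visit 6/12 Month Visit (Day 336 +/- 14 days from Baseline Day 0". A phone contact follows: "The following clinical evaluation will occur 30 days +/- 14 days from study completion (12 Month OCR administration) or premature termination visit". Adverse events are the only item listed for it.
- **Censoring (section 4.9.5).** For both sets, "missing data due to discontinuation will be incorporated as censored time points in the survival analysis of relapse-free patients".
- **Expected result (section 4.9.6).** "Assuming a relapse-free proportion of 0.80 at 12 months, 45 patients are required".

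Sections 3.3.2, 4.9.3, 4.9.5 and 4.9.6 neither give a restriction time for the mean nor call it restricted. Months 3, 6, 9 and 12 are attached to the relapse-free proportion, not to the mean.

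**The concern.** A mean survival time is the area under the whole survival curve, so it can be estimated without a model only if the curve reaches zero. Here the plan expects the curve to stop near 0.80, with about 80% of the times censored. The data then say nothing about the time to relapse of most patients, and the quantity named in the plan is not estimable.

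Software will still print a number, namely the area up to some cut. The cut might be a fixed day, the last follow-up or the last relapse. These give different values, and a reader of the report could not tell which was used or whether it was chosen before the data were seen. A reader could also take the result for an average time to relapse, which it is not. At stake is the meaning of one listed secondary endpoint and its confidence interval, in both analysis sets.

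**Working it through.** **Inputs from the plan.** Relapse-free proportion 0.80 at 12 months, n = 45, 10% attrition and 50 enrolled (section 4.9.6); last relapse assessment on Days 322 to 350 (section 4.5.1).

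**Assumptions not in the plan.** Constant relapse hazard; dropout times uniform over follow-up; month 12 visits uniform over Days 322 to 350.

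**The plan's own figure.** The plan gives no value for the mean. Its sample-size statement reproduces with the plain interval: 0.80 − 1.96 × √(0.80 × 0.20 / 45) = 0.683, in line with "the relapse free proportion is no lower than 0.68, with 95% confidence". So 0.80 is a fair planning value to carry forward.

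**Mean by horizon.** The hazard is λ = −ln(0.80)/336 = 0.000664 per day. The area under the curve to horizon τ is (1 − e^(−λτ))/λ.

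| Horizon τ | Restricted mean at 0.80 |
|---|---|
| Day 322 | 289.9 days |
| Day 336 | 301.2 days |
| Day 350 | 312.3 days |
| No limit (1/λ) | about 1,506 days |

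The last row is extrapolation from the assumed hazard. Across the visit window alone the value moves by 312.3 − 289.9 = 22.4 days, about 7% of 301.2.

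**Relapse timing.** If the 20% relapsing did so uniformly over the first 168 days, the mean to Day 336 would be 336 − 0.20 × (336 − 84) = 285.6 days.

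**Relapsing patients only.** The wording does not exclude a mean over relapsing patients alone. Under the constant hazard that is (301.2 − 336 × 0.80)/0.20 = 162 days.

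**Cut at the last relapse.** In 4,000 simulated trials of 50 at 0.80, the area to the last relapse averaged 269 days (5th to 95th percentile 205 to 310). The area to Day 336 averaged 301 (281 to 319), and to the last follow-up 312. Repeat runs of the last-relapse cut gave 268 to 270.

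Two worked examples, each with 50 patients and no dropout, show how that cut behaves:

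- *It need not rise as results improve.* Ten relapses on Days 33, 66, … 330 (proportion 0.80) give 330 − (3300 − 1815)/50 = 300.3 days. One relapse on Day 40 (proportion 0.98) gives 40 days. To Day 336 the values are 336 − (3360 − 1815)/50 = 305.1 and 40 + 0.98 × 296 = 330.1.
- *It can differ between the analysis sets.* If the Day 330 relapser is excluded from the per-protocol set, 300.3 becomes 297 − (2673 − 1485)/49 = 272.8, while the proportion rises from 40/50 = 0.800 to 40/49 = 0.816. To Day 336 the change is from 305.1 to 336 − (3024 − 1485)/49 = 304.6.

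**Median.** Ignoring dropout, the curve reaches 0.50 only if at least 23 of 45 patients relapse. At 0.80 that probability is P(Bin(45, 0.20) ≥ 23) = 3.3 × 10⁻⁶. The median will almost surely be not reached, which is a normal way to report it and not an error.

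**The case against.** The strongest reply is that month 12 is the obvious horizon. The primary endpoint, the last Kaplan-Meier time point, the sample size and the last relapse assessment all sit there. With the curve taken to the last follow-up, the mean is about 312 days against 301 at Day 336, a gap under 4%. The endpoint is secondary and descriptive, no test or decision uses it, and the relapse-free proportions and the annualized relapse rate are reported too.

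Most of this stands, and it limits the importance of the point. It does not remove it: month 12 is never given as the cut for the mean, the protocol's month 12 is a 28-day window, and even with that cut the quantity is a restricted mean that the plan calls a mean.

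A reader might go further and infer that the reported mean will fall as results improve, or will drop by about 28 days between analysis sets. The documents do not support that. Both effects need a cut at the last relapse, which no section states. The first also compares hypothetical trials, whereas this single-arm trial compares the mean with nothing. In simulation with 3 of 50 patients excluded at random (an assumed number), a shift above 20 days between sets occurred in only 3 to 4% of trials, even with that cut.

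It can also be said that Day 336 is the middle of the visit window and not the shortest planned follow-up. That is fair: at 0.80 about 50 × 0.90 × 0.80 × 0.5 = 18 patients would still be at risk there. Day 322 would be defensible too. What matters is that one fixed day is named in advance.

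**Conclusion.** The point holds as a specification gap with a real consequence. As worded, the mean time to first relapse cannot be estimated from this trial, and any value reported under that name will be a restricted mean with an unstated horizon. At the plan's 0.80 and a constant hazard, the choice moves it from about 290 to 312 days within the visit window, and to about 268 to 270 if the curve were cut at the last relapse. The 0.80 and the visit window come from the plan; the hazard shape, dropout timing and visit spread are assumptions. The conclusion that the mean is not estimable needs only the plan's own expectation that most patients stay relapse-free.

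A reader might infer that the primary analysis or the sample size is undermined. Neither is: the relapse-free proportion at 12 months does not use the mean. The correction is worth making because it is cheap and because the endpoint is promised with a confidence interval.

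**What to change.** In sections 3.3.2 and 4.9.3, replace the mean time to first relapse with:

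> Restricted mean relapse-free time: area under the Kaplan-Meier curve from Day 0 to Day 336, with 95% CI, using the same horizon in both analysis sets. The median is reported as not reached unless the curve falls to 0.50.

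**Cost.** One or two sentences and standard software; no extra patients, visits or data.

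**Downsides to accept.**

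- The figure cannot be quoted as an average time to relapse.
- Relapses on Days 337 to 350 do not enter it. At 0.80 this is about 18 patients × 7 days × 0.000664 = 0.08 relapses expected per trial of 50 (simulated 0.086, so about 0.09). They still count in the annualized relapse rate.
- The confidence interval is approximate when relapses are few. In simulation with n = 50, coverage of the usual normal interval was 91.4% at 0.80 and 85.9% at an assumed 0.95. With no relapses the estimate equals 336 and has no usable interval.

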3. STUDY DESIGN

3.1 DESCRIPTION OF THE STUDY

This is a multicenter, prospective, open-label Phase IV clinical trial. Patients with relapsing forms of MS, ages 18 to 65, who have received a stable dose of NTZ for 12 or more consecutive months, and have been free of relapses, disability worsening or MRI progression 6 months prior to the transition screening visit will be eligible for the study. After informed consent to participate has been obtained, the patient will have a neurological exam, EDSS, 3T or 1.5T MRI, MSIS-29 and labs done for the screening visit to determine eligibility. 3T or 1.5T brain MRI with and without contrast will be performed with the standard MS protocol. It is preferred that the MRIs are done on a 3T scanner for this trial, but not required. MRIs will be performed with 3mm slice thickness with no gaps between slices. Patients will receive their first dose of OCR 4 to 6 weeks after the last dose of NTZ. Other baseline measures, including EDSS, MSIS-29, and labs will be performed within 4 weeks of screening. A neurological exam, EDSS, and labs will be performed at month 3, month 6, month 9, and month 12. MSIS-29 will be performed at months 6 and 12. MRIs will be performed at screening to determine

eligibility and at months 3, 6, and 12. All adverse events will be reported to the study sponsor. OCR will not be provided by the study; the medication will be supplied through the patient's commercial pharmacy and billed to the patient or the patient's insurance.

Patients will receive OCR 4-6 weeks after their last infusion of NTZ. OCR 300mg IV will be given on Day 0 and repeated with the same dose on Day 14±2. Patients will then receive OCR 600mg IV every 24 weeks.

If discontinuation of study drug occurs, the subject may continue in the trial for observational purposes. If willing to continue, they will complete all visit items moving forward, with the exception of study drug dosing and pregnancy testing (if applicable). If study drug is discontinued and the subject is unwilling to continue in the trial, a premature termination visit will be completed as soon as possible.

The target enrollment is 50 patients from 5 centers. Serious adverse events recorded during the trial will be reported to the study sponsor via Medwatch form.

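### Age, EDSS and disease duration would be better tested as continuous variables, and the five unadjusted factor tests under Primary Analysis should be labelled exploratory

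*Combined protocol and SAP*

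**What the plan says.** The Primary Analysis paragraph of section 4.9.3 estimates the relapse-free proportion by Kaplan-Meier. It then adds log-rank tests and curves to "examine effects of center, gender, categorized age, categorized EDSS and duration of disease on survival distribution". That makes five factors. The word categorized is attached to age and EDSS; whether it also covers disease duration is unclear.

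Earlier in 4.9.3 the error level is set once for everything: "All analyses will use two-sided confidence intervals and p-values at the 0.05 significance level". For these tests the plan gives no cut-points, no number of categories, no multiplicity adjustment and no exploratory label.

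Section 4.9.5 describes the same analyses as "log rank tests stratified by age, gender, EDSS, and center". That list has four factors and leaves out disease duration.

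Section 4.9.6 supplies the planning figures: "Assuming a relapse-free proportion of 0.80 at 12 months, 45 patients are required", and "To account for 10% attrition, a total of 50 patients are needed". Section 3.1 adds: "The target enrollment is 50 patients from 5 centers". The documents state no expected number of relapses and no power for the factor tests.

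**The concern.** Age, EDSS and disease duration are recorded as numbers. Putting them into groups treats everyone in a group as alike, so a real gradient is harder to detect. That matters more when events are few, and here about 10 are expected. A method that uses the same data without grouping is available.

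A second, separate matter is status. Five unadjusted tests sit in the paragraph that defines the primary analysis, with nothing to mark them as exploratory. A chance finding for one factor could then be reported as part of the primary result.

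**Working it through.** **Inputs.** Relapse-free proportion 0.80, lower limit 0.68, 45 evaluable and 50 enrolled, 10% attrition (4.9.6); 5 centers (3.1); two-sided 0.05 and five factors (4.9.3); four factors (4.9.5). Assumed, not from the documents: normal covariate, log-linear effect, exponential relapse times, equal centers, 70:30 gender split, and the range of hazard ratios (HRs).

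**1. The plan's own sample size.** With a simple two-sided 95% interval and no censoring, n = p(1−p)z²/d² = 0.80 × 0.20 × 1.96² / 0.12² = 42.7, so 43. That is within 2 of the stated 45. At n = 45 the lower limit is 0.80 − 1.96 × √(0.16/45) = 0.683. Attrition: 45/0.90 = 50. The plan's figures are reproduced closely enough to use.

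**2. Expected first relapses.** 0.20 × 50 = 10, or 0.20 × 45 = 9. Over 5 centers that averages 10/5 = 2 per center, for a test on 4 degrees of freedom.

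**3. Information lost by grouping a normal covariate.**
- Median split: retained 2/π = 0.637, loss 36%.
- Three equal groups with ordered scores: retained 0.793, loss 21%.
- 70:30 split: loss 42%. 80:20 split: loss 51%.

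**4. Power, continuous score test against median-split log-rank.** By formula, the expected test statistic is √D × ln(HR per SD), multiplied by √(2/π) for the split. With D = 10 and HR 2.0: √10 × 0.693 = 2.19, power 59%; 2.19 × 0.798 = 1.75, power 42%. Simulation used n = 50, about 10 events and 3,000 runs per row:

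| HR per SD | Continuous | Median split | Relative loss (simulation) | Relative loss (formula) |
|---|---|---|---|---|
| 1.5 | 25% | 17% | 30% | 30% |
| 2.0 | 56% | 37% | 35% | 30% |
| 2.5 | 75% | 52% | 31% | 23% |
| 3.0 | 89% | 66% | 26% | 15% |

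A separate simulation gave 53% v 35% at HR 2.0 and 23% v 15% at HR 1.5, with type I error near 5% for both tests. In it the relative loss was about 20 to 28% with three ordered groups, and about 25 to 28% for a half-point scale resembling EDSS.

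**5. Chance of at least one false positive if no factor matters.** 1 − 0.95⁵ = 22.6%. Simulating the five tests (5,000 runs, 10% dropout) gave 22.8%, and 22.9% with age, EDSS and duration correlated at 0.4. With the four factors of 4.9.5 it is 1 − 0.95⁴ = 18.5%. In the simulation each test rejected 4.3 to 5.7% of the time, so the standard log-rank test keeps its level acceptably even at about 10 events.

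**6. Context for a binary factor.** An even split with 10 events has 19% power at HR 2 and 41% at HR 3.

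**The case against.** The best defence is that nothing in the trial rests on these tests. Sections 2.1 and 2.2 name no prognostic question, and sections 3.3.1 and 3.3.2 list no such outcome. The verb in 4.9.3 is to examine, and curves accompany the p-values. The Primary Analysis paragraph also covers months 3, 6 and 9 and time to first relapse, which the same section lists as secondary. The heading therefore seems to collect the Kaplan-Meier methods rather than mark everything beneath it as confirmatory. All of this stands, and it keeps the point small.

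Three further objections also stand. Center and gender are categorical by nature, so the loss from grouping does not touch them. The 23% comes from running five tests; it is not caused by grouping, and the fix does not lower it. And for a moderate factor (HR 1.5 per SD) power is poor either way, 25% against 17%, so the change helps without making such a factor reliably detectable.

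A reader might take the wording in 4.9.5 literally, as a stratified log-rank test, which would leave nothing to compare in a single-arm trial. In a missing-data sentence that also covers the Kaplan-Meier analyses, it most naturally means curves and tests by subgroup. Only the missing factor is a real discrepancy.

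The claim that continuous against grouped is mere preference does not stand. The continuous test uses data the plan already relies on, has the same type I error, and has more power under every log-linear effect checked.

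**Conclusion.** The point holds as a cheap improvement to a non-confirmatory analysis. With about 10 expected relapses, grouping age, EDSS and disease duration gives away information. The loss is about 36% of it under a median split, or roughly 25 to 35% of the power at HR 1.5 to 2.5 per SD, and less with three ordered groups. These figures rest on a normal covariate and a log-linear effect; EDSS is ordinal, so for it they are a rough guide. Separately, the five tests carry about a 23% family-wise chance of a false finding when no factor matters.

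Three stronger readings are not supported:
- **The plan loses a third of its power.** The plan states no cut-points or number of groups, so it fixes no single figure.
- **The primary result is at risk.** The month-12 relapse-free proportion and its confidence interval do not depend on these tests. The risk is only that a chance factor effect is reported with primary status.
- **Cut-points will be chosen after seeing outcomes.** The plan is silent on cut-points, but nothing in it points to a search for them.

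**What to change.** In section 4.9.3:
- Test age, EDSS and disease duration as continuous variables, one at a time, in Cox models (score or likelihood-ratio test), reporting the hazard ratio with its 95% confidence interval.
- Keep log-rank tests for gender and center. Permutation p-values are not needed.
- Use Kaplan-Meier curves by category for display only, split at the sample median.
- Label all five factor analyses exploratory, with unadjusted p-values, and state that no factor effect will be claimed as a primary result.

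In section 4.9.5, add disease duration to the factor list, so that the complete-case rule covers it and the two sections agree.

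The cost is wording only; no new data are needed. The one statistical downside is that a linear term can miss a U-shaped effect. The family-wise error stays near 23%; the label tells the reader how to weigh it.
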